### 9.10.10 Exploratory Endpoint 1 – PK and ADA Evaluation, Cohorts 1-2

To evaluate the exploratory objective, to evaluate pharmacokinetic (PK) parameters to ensure ADA evaluation adequate of the two lots (Cohorts 1-2), exploratory endpoint #1 will be used:

PK summaries will include NX01, NX02, NX11, XB10, XB18, and XB23 mABs. The following PK parameter estimates for sample tested by ECLA or ELISA will be calculated and summarized using descriptive statistics by dose (where applicable):

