PK samples will be collected for all subjects. Analysis will be completed by electrochemiluminescence assay (ECLA) or enzyme-linked immunosorbent assay (ELISA).

Samples for subjects in Cohorts 1-3 will be tested at pre-dose, 24 hours and 72 hours post-dose, and on Days 8, 15, 45 (before repeat-dose or placebo), 49, 90, and 120. The first 25 subjects randomized for each DP lot of 50 mg and 100 mg doses and placebo will be tested at all timepoints.

All subjects in Cohort 4 will have samples collected at pre-dose, 2 hour, 4 hours, 8 hours, 24 hours, 72 hours post dose, and on Days 8, 15, 30, 45, 90, and 120. Samples will be analyzed for the first 30 subjects in Cohort 4, who receive active drug and complete sample collection at 24 hours. See [Figure 2](#) and [Figure 3](#).

ADA Analysis

ADA will be evaluated by ECLA at pre-dose and on Days 15, 45 (before repeat-dose or placebo), 60, 90, 120, 150, 180, and 240 for study subjects in Cohorts 1-3; and at pre-dose and post dose on Days 90 and 120 for subjects in Cohort 4. See [Figure 2](#) and [Figure 3](#).

Figure 2: Cohort 4 Assessments

[figure not shown]
[figure not shown]

Figure 3: Study Design

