## Statistical Analysis Plan (SAP)

		confidence interval (CI) for GM, the geometric coefficient of variation (GCV, presented in percentage, GCV%), and the 95% CI of GCV% calculated for each time point for each cohort and DP lot
Secondary Objective #3: For Cohort 4 (only active IP): Demonstrate target protective concentration (NAC) value of BoNT/A and BoNT/B at 2 hours post-dose	Secondary Endpoint #3: To evaluate the proportion of subjects with target protective concentration (NAC) value > 0.02 U/mL (botulinum neurotoxin [BoNT]/A) or > 0.03 U/mL (BoNT/B) at 2 hours post dose	Protective NAC rate at 2 Hours post dose, where protective NAC rate is defined as the proportion of subjects with NAC value > 0.02 U/mL against BoNT/A or NAC value > 0.03 U/mL against BoNT/B
Secondary Objective #4: For Cohort 4 (only active IP): To assess pharmacokinetics (PK) at pre-dose through end of study	Secondary Endpoint #4: PK analysis at the determined timepoints	Summary statistics [number of subjects (n), mean, SD, median, first quartile, third quartile, minimum, maximum], CV%, GM, the 95% CI for GM, GCV%, and the 95% CI of GCV% calculated for each time point for the Cohort 4 active G03-52-01 treatment group
Secondary Objective #5: For Cohort 4 (only active IP): To evaluate pharmacodynamics (PD) and anti-drug antibody (ADA) at pre-dose through the end of study	Secondary Endpoint #5: Descriptive statistics of determined PD and ADA timepoints	Summary statistics [number of subjects (n), mean, SD, median, first quartile, third quartile, minimum, maximum], CV%, GM, the 95% CI for GM, GCV%, and the 95% CI of GCV% calculated for each time point for the Cohort 4 active G03-52-01 treatment group
Exploratory Objective	Exploratory Endpoint	Statistical Methodology
Exploratory Objective: For Cohorts 1-3 (Cohorts 1-2 active IP and Cohort 3 is placebo): To evaluate PK parameters to ensure ADA evaluation adequate of the two lots	Exploratory Endpoint: Descriptive statistics of selected PK parameters at all time points tested of the two lots	Summary statistics [number of subjects (n), mean, SD, median, first quartile, third quartile, minimum, maximum], CV%, GM, the 95% CI for GM, GCV%, and the 95% CI of GCV% calculated for each time point for each cohort and DP lot

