## Statistical Analysis Plan (SAP)

---

```
var x;  
ods select ConfLimits;  
run;
```

, where `indata` is the data set with PD parameters and `x` is a parameter.

Additionally, PD parameters and NAC values will be listed separately at the subject level.

The PD population will be used for all pharmacodynamic tables, listings, and figures.

Immunogenicity (ADA) samples will be tested at Baseline/Dosing [Visit 2 (Day 1)] pre-dose, Visit 3 (24 Hours) and Visit 4 (72 Hours) post-dose, and at Visit 5 (Day 8), Visit 6 (Day 15), Visit 7 (Day 45) pre-dose, Visit 8 (Day 49), Visit 10 (Day 90), Visit 11 (Day 120), Visit 12 (Day 150), Visit 13 (Day 180), and Visit 14 (Day 240).

The frequency and percentage of subjects with a positive immunogenicity response will be summarized by time point across the active treatment arms. Additionally, anti-drug antibody titers will be summarized using continuous descriptive statistics [number of subjects (n), mean, SD, median, Q1, Q3, minimum, maximum, CV%, GM, GCV%, and the 95% CI of the GCV] by time point. Both the categorical and continuous ADA table summaries will include a subgroup analysis for only those subjects that have a negative immunogenicity response at baseline. Anti-drug antibody status and titer values will be listed by subject and time point.

The ITT population will be used for all immunogenicity summaries.

### 9.10.7 Secondary Endpoint 3 – Target Protective NAC (2 Hours), Cohort 4

To evaluate secondary objective #3, demonstrate target protective concentration (NAC) value of BoNT/A and BoNT/B at 4 and 8 hours post-dose (Cohort 4), secondary endpoint #3 will be used.

To evaluate the proportion of subjects with target protective concentration (NAC) value > 0.02 U/mL (botulinum neurotoxin [BoNT]/A) or > 0.03 U/mL (BoNT/B) at 2 hours post dose

At the 4 Hour and 8 Hour post-dose time points, the frequency and percentage of subjects with a NAC > 0.02 U/mL against BoNT/A, a NAC > 0.03 against BoNT/B, and those with either a NAC > 0.02 U/mL against BoNT/A or a NAC > 0.03 U/mL against BoNT/B will be presented. Percentages will be based on the total number of subjects at the respective time point with evaluable concentrations.

The PD population will be used for the analysis of this secondary endpoint.

### 9.10.8 Secondary Endpoint 4 – PK Evaluation, Cohort 4

To evaluate secondary objective #4, to assess pharmacokinetics (PK) at pre-dose through end of study (Cohort 4), secondary endpoint #4 will be used.

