## Statistical Analysis Plan (SAP)

---

- $AUC_{(0-t)}$ : Area under the concentration time-curve to the last concentration above the lower limit of quantitation (reported in day\*ng/mL)
- $AUC_{(0-\infty)}$ : Area under the concentration time-curve extrapolated to infinity (reported in day\*ng/mL)
- $C_{max}$ : Maximum observed concentration (reported in ng/mL)
- $Kel$ : Elimination rate constant (reported in 1/day)
- $t_{1/2}$ : Terminal elimination half-life (reported in days)
- $CL/F$ : Total clearance (reported in L/day)
- $V_d/F$ : Volume of distribution (reported in L)

Concentrations of each mAb will be summarized descriptively in tables by active treatment group and time point. Concentration-time profiles will be displayed graphically on linear and semi-log scales by mAb and active treatment group. One set of plots will include error bars (presented as SD) and one set will not include error bars.

The summary statistics used for all PK parameters and concentrations will include number of subjects (n), mean, SD, median, Q1, Q3, minimum, maximum, CV%, GM, 95% CI of the GM, GCV%, and the 95% CI of the GCV.

Additionally, PK parameters and concentrations will be listed separately at the subject level.

The PK population will be used for all pharmacokinetic tables, listings, and figures.

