## Statistical Analysis Plan (SAP)

4. Symptom-directed only.
5. Vital Signs to include sitting diastolic and systolic BP, HR, and oral temperature. Vital signs will be checked just before injection on Day and Day 45 and every visit.
6. Chemistry panel that will include serum creatinine, BUN, calcium, total bilirubin, alkaline phosphatase, ALT, AST, sodium, potassium, albumin, PT, PTT, INR, total CK, carbon dioxide, and chloride. Subjects should be fasting for the chemistry panel.
7. A CBC with differential will be obtained including WBC, RBC, hemoglobin, hematocrit, platelet count, MCV, MCH, MCHC, RDW, MPV, neutrophils, lymphocytes, monocytes, eosinophils, and basophils.
8. A serum pregnancy test will be obtained at screening for all women of reproductive capacity. A urine pregnancy test will be obtained and must be resulted prior to Day 1 dosing. Results must be confirmed as negative before study product is dosed.
9. Urine drug screening.
10. A urine dipstick will be done to evaluate for presence of protein, glucose or blood in urine. If dipstick is abnormal (>+1), a complete urinalysis with microscopic will be performed.
11. A 12-lead ECG will be done during screening. Subjects with a QTc interval >450 milliseconds will be excluded from participation.
12. Viral Serology includes HIV, HBsAg and antibody to HCV.
13. Serum from subjects who give consent will be stored for future use on Days 0, 8, and 30.
14. The Hypersensitivity Panel includes cytokine and complement panels, IgE, and tryptase. Refer to lab manual for further processing instructions. . .
15. PK samples will be collected for all subjects by ECLA or ELISA at pre-dose, 24 hours and 72 hours post dose, and on Days 8, 15, 45 (before repeat-dose or placebo), 49, 90, and 120.
16. Serological samples (PD) will be collected for all subjects by MNA for serotypes A and B at pre-dose, 24 hours post dose, and on Days 8, 15, 45 (before repeat-dose or placebo), 49, 90, and 120.
17. ADA samples will be collected and tested for all subjects at pre-dose and Days 15, 45 (before repeat-dose or placebo), 60, 90, 120, 150, 180, and 240.
18. Samples to be collected pre-dose prior to Day 45 repeat dose.

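### The exploratory objective is to use PK to ensure the ADA evaluation is adequate, but no planned output relates drug level to ADA result

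*SAP*

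**What the plan says.** Protocol 4.1 and SAP 2.3 set one exploratory objective for Cohorts 1-3, which SAP 9.10.10 restates as "to evaluate pharmacokinetic (PK) parameters to ensure ADA evaluation adequate of the two lots (Cohorts 1-2". The endpoint attached to it in SAP Section 5, Table 2 is "Descriptive statistics of selected PK parameters at all time points tested of the two lots", which has no ADA term.

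SAP 9.10.10 is headed PK and ADA Evaluation. Its plan consists of PK parameters for the six antibodies, concentration-time plots, a PK listing, and this: "Concentrations of each mAb will be summarized descriptively in tables by active treatment group and time point". Apart from the restated objective, ADA is not mentioned in its text.

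ADA is handled in SAP 9.10.6: "The frequency and percentage of subjects with a positive immunogenicity response will be summarized by time point across the active treatment arms". That section adds titers, a baseline-negative subgroup and a listing. It uses the ITT population, while SAP 9.10.10 uses the PK population.

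Sampling in Cohorts 1-3:
- ADA, Protocol 5.1: "ADA will be evaluated by ECLA at pre-dose and on Days 15, 45 (before repeat-dose or placebo), 60, 90, 120, 150, 180, and 240". SAP Appendix A agrees: "at pre-dose and Days 15, 45 (before repeat-dose or placebo), 60, 90, 120, 150, 180, and 240".
- PK, SAP Appendix A: "at pre-dose, 24 hours and 72 hours post dose, and on Days 8, 15, 45 (before repeat-dose or placebo), 49, 90, and 120".
- ADA, SAP 9.10.6, differently: "Immunogenicity (ADA) samples will be tested at Baseline/Dosing [Visit 2 (Day 1)] pre-dose, Visit 3 (24 Hours) and Visit 4 (72 Hours) post-dose". It continues with Days 8, 15, 45, 49, 90, 120, 150, 180 and 240, without Day 60.

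Protocol 8.6.3 and SAP 3.4 describe the ADA assay as a validated ECLA for total ADA. Neither gives a drug-tolerance limit.

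**The concern.** An analysis that leaves ADA out cannot show that the ADA evaluation is adequate. The natural reading of the objective is a check that circulating drug does not hide antibodies from the assay. That reading is an inference, since the documents never mention interference, but the gap exists on any reading.

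The question is a live one here because the trial expects drug to be present at ADA visits. Its neutralizing-concentration targets are set for Days 45 and 90 (primary) and Day 120 (secondary), and ADA is drawn on those same days. If the ECLA loses sensitivity at those drug levels, ADA incidence would be understated there. A rise at Days 150 to 240 could then be late seroconversion or unmasking, and the planned tables could not separate the two.

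**Working it through.** The documents state no sample size or power figure for this endpoint, so the check is a match of schedules and a count.

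**1. Planned outputs.** SAP 9.10.10 and Table 2 give PK only. SAP 9.10.6 gives ADA only. The subject-level listings are separate. No table, figure or model sets ADA status against concentration, and no inconclusive category is defined.

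**2. Matching the days (post-dose, Cohorts 1-3).**

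| ADA list | ADA times | With PK | Without PK |
|---|---|---|---|
| Protocol 5.1, SAP Appendix A | 8 | Days 15, 45, 90, 120 | Days 60, 150, 180, 240 (4/8 = 50%) |
| SAP 9.10.6 | 11 | 24 h, 72 h, Days 8, 15, 45, 49, 90, 120 | Days 150, 180, 240 (3/11 = 27%) |

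The visit-by-visit schedule in Protocol 9.1 agrees with the first row. It draws ADA but not PK on Days 60, 150, 180 and 240, and PK but not ADA at 24 h, 72 h and Days 8 and 49. Up to Day 120, the SAP 9.10.6 list coincides with the PK list.

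**3. Subjects.** PK is tested in 25 subjects per dose/lot group (Protocol 5.1, SAP 3.4). This agrees with the 2:1 PD:PK split in Protocol 5.4.2: 75 × 1/3 = 25. Active subjects with PK: 4 × 25 = 100 of 300. ADA is tested in all subjects.

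**4. Active subject-times in Cohorts 1-2 that can be paired.**
- Protocol/Appendix A: (100 × 4) / (300 × 8) = 400 / 2,400 = 16.7%.
- SAP 9.10.6 list: (100 × 8) / (300 × 11) = 800 / 3,300 = 24.2%.

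**5. Cohort 4.** Post-dose ADA falls on Days 90 and 120, and both days have PK. PK is tested in 30 of 200 active subjects: (30 × 2) / (200 × 2) = 60 / 400 = 15%.

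**6. Which unpaired visits matter (illustration only).** The documents give no half-life. I assume h = 14 to 42 days, instant absorption and doses on Days 1 and 45. The level as a fraction of one dose's peak is 0.5^((d−1)/h), plus 0.5^((d−45)/h) after Day 45.

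| Day | h = 14 | h = 28 | h = 42 |
|---|---|---|---|
| 60 | 53% | 92% | 116% |
| 90 | 12% | 44% | 71% |
| 120 | 2.7% | 21% | 43% |
| 150 | 0.6% | 9.9% | 26% |
| 180 | 0.1% | 4.7% | 16% |
| 240 | 0.01% | 1.1% | 5.9% |

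Day 60, the first ADA sample after re-dosing on the Appendix A schedule, is the unpaired visit with the most drug on board. Days 150 to 240 have the least.

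**The case against.** The best defence is that SAP 9.10.10 delivers the endpoint as defined, which is descriptive PK by lot, in an exploratory part of a trial with no formal testing. Concentrations by dose/lot group are planned at ADA Days 15, 45, 90 and 120 and could be set beside the assay's tolerance. PK and ADA are both listed by subject, so a manual comparison is possible. Three of the four unpaired visits are late, when masking is least likely, and Day 60 is bracketed by PK on Days 49 and 90.

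Much of this stands. It makes the gap easy to close, but possible manual work is not a planned analysis. The plan names no tolerance limit and no rule for a negative found with drug above it.

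A reader might go further in three ways that the documents do not support:
- **That masked negatives are being reported as true negatives.** The assay is a validated total-ADA method whose tolerance is not given. The SAP reports the percentage positive and never calls the remainder true negatives.
- **That half the ADA visits lack PK, without qualification.** This holds on the protocol/Appendix A schedule, not on the SAP 9.10.6 list.
- **That Cohort 4 has the same timing gap.** It does not. Its limit is that only 30 active subjects have PK tested.

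**Conclusion.** The point holds as a gap between an objective and its analysis: nothing planned relates drug level to ADA result, so the adequacy of the ADA evaluation would go unexamined. On the protocol/Appendix A schedule, 4 of 8 post-dose ADA times are unpaired and about 17% of active ADA subject-times in Cohorts 1-2 can be paired. On the SAP 9.10.6 list the figures are 3 of 11 and about 24%. These are planned counts and assume no missed samples.

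The size of any bias in ADA incidence cannot be stated. It depends on a tolerance limit and drug levels that the documents do not give, and the half-life range above is my assumption. Even the contrast between visits is sensitive to it: Day 60 against Day 240 is about 20-fold at 42 days (116/5.9) and about 86-fold at 28 days (92.19/1.07). Relative levels alone do not show that any sample was masked.

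**What to change.** 1. Add one table to SAP 9.10.10, for PK-tested subjects by dose and lot, at Days 15, 45, 90 and 120. Show the drug concentration and classify ADA as positive, negative with drug at or below the assay's validated tolerance, or negative with drug above tolerance (inconclusive). State whether the tolerance applies to each antibody or to the total product.
2. Give the same table for the 30 PK-tested Cohort 4 subjects at Days 90 and 120.
3. Keep the all-subject ADA tables as planned. Add a note that drug level was not assessed at unpaired visits or in subjects without PK testing.
4. Reconcile the ADA times in SAP 9.10.6 with Protocol 5.1 and SAP Appendix A.
5. Do not project drug levels to Days 150-240. After the second dose an individual elimination rate would rest on three samples (Days 49, 90 and 120), too thin a basis for extrapolating to Day 240.

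The cost is one or two tables from data already planned, plus the tolerance limit from the assay validation. The downside is that some results now counted simply as negative become inconclusive, so the ADA statement may read slightly less favourably.

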## Statistical Analysis Plan (SAP)

---

- $AUC_{(0-t)}$ : Area under the concentration time-curve to the last concentration above the lower limit of quantitation (reported in day\*ng/mL)
- $AUC_{(0-\infty)}$ : Area under the concentration time-curve extrapolated to infinity (reported in day\*ng/mL)
- $C_{max}$ : Maximum observed concentration (reported in ng/mL)
- $Kel$ : Elimination rate constant (reported in 1/day)
- $t_{1/2}$ : Terminal elimination half-life (reported in days)
- $CL/F$ : Total clearance (reported in L/day)
- $V_d/F$ : Volume of distribution (reported in L)

Concentrations of each mAb will be summarized descriptively in tables by active treatment group and time point. Concentration-time profiles will be displayed graphically on linear and semi-log scales by mAb and active treatment group. One set of plots will include error bars (presented as SD) and one set will not include error bars.

The summary statistics used for all PK parameters and concentrations will include number of subjects (n), mean, SD, median, Q1, Q3, minimum, maximum, CV%, GM, 95% CI of the GM, GCV%, and the 95% CI of the GCV.

Additionally, PK parameters and concentrations will be listed separately at the subject level.

The PK population will be used for all pharmacokinetic tables, listings, and figures.

## 10 Changes to Planned Analysis from Study Protocol

N/A

## Statistical Analysis Plan (SAP)

### 11 Appendix

#### 11.1 Appendix A. Schedule of Assessments

Cohorts 1-3:

Study Visit	Screening 	Baseline/ Dosing 		3	4	5	6	7	8	9	10	11	12	13	14	Unscheduled
		D 1	1- Hour Stay													
Day of Study	-14 to -1															
Visit Windows																
Review Inc/Excl Criteria	X	X														
Demographics	X															
Review Medical History	X	X														
Randomization		X														
Study Drug Administration		X						X								
Concomitant Medications 	X	X	X	X	X	X	X	X	X	X	X	X	X	X	X	X
AE/SAE Review		X	X	X	X	X	X	X	X	X	X	X	X	X	X	X
Physical Exam 	X	X	(SD) 	SD												
Vital Signs 	X	X	X	X	X	X	X	X	X	X	X	X	X	X	X	X
CBC with differential 	X	X	X	X	X	X	X	X	X	X	X	X	X	X	X	X
Chemistry 	X	X	X	X	X	X	X	X	X	X	X	X	X	X	X	X

## Statistical Analysis Plan (SAP)

Study Visit	Screening 	Baseline/ Dosing 		3	4	5	6	7	8	9	10	11	12	13	14	Unscheduled
		D 1	1- Hour Stay													
Day of Study	-14 to -1			24 Hours (±2 hrs)	72 Hours (±2 hrs)	D 8 (±1D)	D 15 (±2D)	D 45 (±3D)	D 49 (±3D)	D 60 (±3D)	D 90 (±3D)	D 120 (±3D)	D 150 (±3D)	D 180 (±3D)	D 240 (±5D)	Unscheduled
Visit Windows																
Serology Panel 	X															
Pregnancy Test 	X (serum)	X (urine)						X (urine)							X (urine)	
Drug Screening 	X	X						X								
Breathalyzer test	X	X						X								
Urine Dipstick 	X	X						X							X	
12-lead ECG 	X						X									
PK samples 		X		X	X	X	X	X 	X		X	X				
MNA samples 		X		X		X	X	X 	X		X	X				
Immunogenicity (ADA) samples 		X					X	X 		X	X	X	X	X	X	
Future Use Sample 		X					X	X 		X	X	X	X	X	X	
Hypersensitivity Panel 		X						X								
Subject Diary Review 			X	X	X	X		X	X	X						

1. Screening will be completed within 14 days prior to administration of study drug and may require more than one visit.
2. Concomitant medications including all of the following: prescription drugs, over-the-counter drugs, herbs, vitamins, nutritional supplements, illicit and recreational substance use, birth control information.
3. PE includes height and weight at screening.

## Statistical Analysis Plan (SAP)

4. Symptom-directed only.
5. Vital Signs to include sitting diastolic and systolic BP, HR, and oral temperature. Vital signs will be checked just before injection on Day and Day 45 and every visit.
6. Chemistry panel that will include serum creatinine, BUN, calcium, total bilirubin, alkaline phosphatase, ALT, AST, sodium, potassium, albumin, PT, PTT, INR, total CK, carbon dioxide, and chloride. Subjects should be fasting for the chemistry panel.
7. A CBC with differential will be obtained including WBC, RBC, hemoglobin, hematocrit, platelet count, MCV, MCH, MCHC, RDW, MPV, neutrophils, lymphocytes, monocytes, eosinophils, and basophils.
8. A serum pregnancy test will be obtained at screening for all women of reproductive capacity. A urine pregnancy test will be obtained and must be resulted prior to Day 1 dosing. Results must be confirmed as negative before study product is dosed.
9. Urine drug screening.
10. A urine dipstick will be done to evaluate for presence of protein, glucose or blood in urine. If dipstick is abnormal (>+1), a complete urinalysis with microscopic will be performed.
11. A 12-lead ECG will be done during screening. Subjects with a QTc interval >450 milliseconds will be excluded from participation.
12. Viral Serology includes HIV, HBsAg and antibody to HCV.
13. Serum from subjects who give consent will be stored for future use on Days 0, 8, and 30.
14. The Hypersensitivity Panel includes cytokine and complement panels, IgE, and tryptase. Refer to lab manual for further processing instructions. . .
15. PK samples will be collected for all subjects by ECLA or ELISA at pre-dose, 24 hours and 72 hours post dose, and on Days 8, 15, 45 (before repeat-dose or placebo), 49, 90, and 120.
16. Serological samples (PD) will be collected for all subjects by MNA for serotypes A and B at pre-dose, 24 hours post dose, and on Days 8, 15, 45 (before repeat-dose or placebo), 49, 90, and 120.
17. ADA samples will be collected and tested for all subjects at pre-dose and Days 15, 45 (before repeat-dose or placebo), 60, 90, 120, 150, 180, and 240.
18. Samples to be collected pre-dose prior to Day 45 repeat dose.
19. Subjects will be provided a reactogenicity diary prior to leaving the clinic on baseline/dosing Day 1. Subjects will be asked to complete daily diary records study Day 1-7 and dairy is to be collected by site staff on Day 8 for review. Subjects will be provided a reactogenicity diary prior to leaving the clinic on baseline/dosing Day 45. Subjects will be asked to complete daily diary records study Day 46-52 and dairy is to be collected by site staff on Day 60 for review.

